9.3 STATISTICAL ANALYSES

9.3.1 General Approach

A formal statistical analysis plan (SAP) and data management plan will be developed and finalized before study database lock. The following is a summary of statistical approach:

- Variables used for sample size calculation will be calculated and presented for pooled populations and each subject population.
- All disposition, demographic, baseline characteristic and concomitant medication summaries will be presented by arm.
- Continuous variables: Descriptive statistics will include the number of non-missing values (n), arithmetic mean, standard deviation (SD), median, minimum and maximum

values. 90% Confidence Intervals (CIs), least-square (LS Means) values and Ratio for Geometrics LS means will also be displayed when appropriate.

- Categorical variables: Descriptive statistics will include counts and percentages per category. The denominator in all percentage calculations will be the number of subjects in the relevant analysis population with non-missing data, unless specifically stated otherwise. Percentages will be displayed to one decimal place. Proportions will be displayed to 3 decimal places.

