1.1 Changes from Protocol

The visit window for analysis was changed from +2 days to +6 days.

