6 STATISTICAL ANALYSIS METHODS

No formal statistical tests or inference will be performed. All summaries will be presented using descriptive statistics for each cohort, and overall. Data processing, summarization, and analyses will be performed using SAS Version 9.4 or higher. Unless otherwise discussed, continuous variables will be summarized by the number of available data points (N), mean, standard deviation, median, minimum, and maximum. 90% confidence intervals, least-square means, and ratio for geometrics LS means will be displayed when appropriate. The mean, median, minimum, and maximum will be displayed with the same number of decimals as raw data, and the standard deviation will be displayed with two more decimals than raw data. Categorical variables will be summarized by the number and percentage of subjects in each level, where the denominator for each percentage is the number of subjects in the relevant population and specified cohort. Percentages will be displayed to one decimal place and proportions will be displayed to three decimal places. Data listings of all data collected on the eCRF will be presented, sorted by subject number and visit, where applicable.

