6.3 Missing Data and Imputation

There will be no imputation of missing data.

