6.7.1 Electrocardiogram (ECG)

Baseline, post-dose, and change from baseline for ECG parameters (heart rate (HR), RR interval, QRS interval, PR interval, QT interval, and QTcF) along with clinically significant abnormalities on T and U waves will be presented by cohort and overall. Triplicate ECGs will be conducted on Day 1 (at pre-dose, 90 minutes post-dose, and 8 hours post dose) and single ECGs at other timepoints. Results will also be listed by subject ID.

Clinically significant findings will be presented based on the following categories:

- The proportion of patients obtaining a heart rate change from baseline > 25% decrease resulting in a heart rate < 50 beats per minute (bpm) and heart rate change from baseline > 25% increase resulting in a heart rate > 100 bpm.
- The proportion of patients obtaining a QRS change from baseline > 25% increase resulting in QRS > 120 ms.
- The proportion of patients obtaining a PR interval change from baseline > 25% increase reaching a value of > 220 ms.
- The proportion of patients obtaining a QTcF increase from baseline values > 30 ms and ≤ 60 ms; and > 60 ms.
- The proportion of patients obtaining treatment emergent absolute QTcF values > 450 ms and ≤ 480 ms; > 480 ms and ≤ 500 ms; and > 500 ms.

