6.11.2 Ophthalmoscopy

Measurements will be taken of the vitreous, macula, peripheral retina, choroid, optic nerve for both eyes and assessed on a scale of normal, abnormal (NCS), abnormal (CS), and not done.

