6.11.3 Slit Lamp Biomicroscopy

Measurements will be taken of the subject's lids/lashes, conjunctiva/sclera, iris/pupil, cornea, anterior chamber, and lens at each protocol specified timepoint for both eyes and assessed on a scale of normal, abnormal (NCS), abnormal (CS), and not done.

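### SAP 6 drops the protocol's non-missing condition from percentage denominators without declaring it, which dilutes the ECG threshold proportions when values are missing

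*SAP*

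**What the plan says.** Protocol 9.3.1 sets one rule for the whole study: "The denominator in all percentage calculations will be the number of subjects in the relevant analysis population with non-missing data, unless specifically stated otherwise".

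SAP 6 sets another for categorical variables: "where the denominator for each percentage is the number of subjects in the relevant population and specified cohort". It has no non-missing condition. In the same paragraph continuous variables are handled differently: "continuous variables will be summarized by the number of available data points (N), mean, standard deviation, median, minimum, and maximum".

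SAP 1.1 lists a single change from the protocol: "The visit window for analysis was changed from +2 days to +6 days".

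The outputs that the denominator can reach are:

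- **ECG (SAP 6.7.1).** Results are reported as proportions of patients beyond a limit, for example "The proportion of patients obtaining a QTcF increase from baseline values > 30 ms and ≤ 60 ms; and > 60 ms". No missing category is defined.
- **Ophthalmoscopy (SAP 6.11.2).** Findings are recorded "for both eyes and assessed on a scale of normal, abnormal (NCS), abnormal (CS), and not done". SAP 6.11.3 uses the same four levels for the slit lamp.
- **Laboratory (SAP 6.7.4).** Results are summarised by cohort and time point. No table of abnormality percentages is defined.
- **Adverse events (SAP 6.7, with population in 4.1).** Incidence is taken over dosed subjects.

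**The concern.** Two governing documents give different general denominators, and a programmer working from the SAP would not learn that the protocol differs. The SAP rule keeps a subject with no value in the denominator, while that subject cannot enter the numerator. For a safety threshold the error runs in the reassuring direction. Elsewhere the SAP leans the other way: under 6.7 a missing AE severity or relationship takes the most cautious value.

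The SAP is also uneven within itself. The same QTcF data could appear with N = 10 in the change-from-baseline summary and be divided by 12 in the threshold table.

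Safety is the primary objective. Protocol 2.3.1 lists cardiovascular effects, including hERG inhibition in vitro, among the potential risks, so the ECG proportions will be read closely.

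**Working it through.** The plan states no figure that depends on the denominator, so there is nothing to reproduce.

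**Inputs**

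- Denominator rules: protocol 9.3.1 and SAP 6.
- Cohort sizes: 3-9 for cohorts 1-2 and 12 for cohorts 3-4 (SAP 3); about 36 in total (SAP 3.1).
- Number with the finding, x, and number without a usable value, m: assumed, because the documents give no missing-data rate.
- SAP 6.7.1 speaks of proportions and SAP 6 of percentages. I assume the SAP 6 denominator applies, since 6.7.1 gives no other.

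**Formulas**

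- SAP percentage = x / n
- Protocol percentage = x / (n - m)
- Ratio of SAP to protocol = (n - m) / n

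**Threshold proportions**

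| n | x | m | SAP rule | Protocol rule |
|---|---|---|---|---|
| 3 | 1 | 1 | 1/3 = 33.3% | 1/2 = 50.0% |
| 9 | 1 | 1 | 1/9 = 11.1% | 1/8 = 12.5% |
| 9 | 1 | 2 | 1/9 = 11.1% | 1/7 = 14.3% |
| 12 | 1 | 1 | 1/12 = 8.3% | 1/11 = 9.1% |
| 12 | 1 | 4 | 1/12 = 8.3% | 1/8 = 12.5% |
| 36 | 3 | 1 | 3/36 = 8.3% | 3/35 = 8.6% |
| 36 | 3 | 4 | 3/36 = 8.3% | 3/32 = 9.4% |

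With m = 0 the rules agree in every row.

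**Eye examination, one eye.** Assume n = 12, with 8 normal, 1 abnormal (NCS), 1 abnormal (CS) and 2 not done, and treat 'not done' as missing under the protocol rule.

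| Level | SAP rule | Protocol rule | If missing were counted as normal |
|---|---|---|---|
| Normal | 8/12 = 66.7% | 8/10 = 80.0% | 10/12 = 83.3% |
| Abnormal (NCS) | 1/12 = 8.3% | 1/10 = 10.0% | 1/12 = 8.3% |
| Abnormal (CS) | 1/12 = 8.3% | 1/10 = 10.0% | 1/12 = 8.3% |
| Not done | 2/12 = 16.7% | not in denominator | 0% |

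The SAP rule dilutes the abnormal levels, but it dilutes the normal level too and shows the gap openly. For the ECG thresholds only the share beyond the limit is defined. There, a missing subject has the same effect on the reported figure as a subject without the finding.

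**Outputs not affected.** Every dosed subject belongs in the denominator for AE and SAE incidence. Numeric laboratory, vital-sign and intraocular pressure summaries use the available N. At most, categorical laboratory items such as some urinalysis results could be touched.

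**The case against.** **The protocol allows stated exceptions.** This does not clearly cover the change. SAP 6 does not name an exception for particular tables; it replaces one general rule with another, and SAP 1.1 is silent.

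**The ECG categories may not be per time point.** SAP 6.7.1 does not say. If they mean any post-dose occurrence, a subject who misses Day 8 but has the 90-minute and 8-hour ECGs is still evaluable, and the rules would usually agree. The Day 1 ECGs also fall within the 8-hour confinement (protocol 1.3), and the SAP accepts follow-up visits from Day 8 to Day 14. This stands as a reason to expect m to be small. It does not make the rules the same.

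**Little turns on the figures.** No hypothesis tests are planned, counts accompany percentages, and ECG results are listed by subject. The SMC works from a safety summary and an AE table (protocol 10.1.5), and the interim analysis uses subject listings (SAP 7). No documented decision rests on the affected percentages. This stands, and it sets the severity.

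A reader might also infer more than the documents support:

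- *Every percentage is wrong.* The SAP 6 sentence covers categorical variables, and for AE incidence its denominator is the suitable one.
- *A missing eye or laboratory result counts as normal.* The eye examinations have a separate level for it: the slit lamp is graded "at each protocol specified timepoint for both eyes and assessed on a scale of normal, abnormal (NCS), abnormal (CS), and not done". For the laboratory, no abnormality percentage is defined.
- *The rule contradicts SAP 6.3*, which says "There will be no imputation of missing data". A denominator convention fills in no value. The resemblance is one of effect, and only for the ECG thresholds.
- *The bias is inherently worse in small cohorts.* The factor depends on the missing fraction, not on cohort size. A small cohort suffers more only in that one missing subject is a larger fraction of it.

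**Conclusion.** The mismatch is real and undeclared. Applied as written, the SAP multiplies the protocol's percentage by (n-m)/n. This bears mainly on the ECG threshold proportions and, less seriously, on abnormal eye-examination percentages.

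On the assumed counts the gap is 16.7 percentage points in a cohort of 3 with one missing, 0.8 to 4.2 points in a cohort of 12 with one to four missing, and about 1 point across 36 subjects with three findings and four missing. It is zero if data are complete.

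The conclusion on the ECG rests on two assumptions: that the SAP 6 denominator governs 6.7.1, and that some subjects lack a needed baseline or post-dose value. Severity is minor.

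**What to change.** In SAP 6, replace the single denominator rule with two sentences:

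1. AE, SAE, disposition and medication percentages use all subjects in the relevant population and cohort.
2. ECG threshold categories, and any other by-time-point or change-from-baseline category, use subjects with the values needed (including a baseline where change is involved). The table prints the number assessed and the number missing.

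The second sentence restores the protocol's own rule. List in SAP 1.1 any departure from protocol 9.3.1 that remains. When applying the rule, SAP 6.7.1 should also say whether each ECG category is per time point or any post-dose occurrence, because that decides who counts as assessed.

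The cost is two sentences and some table-shell headers, with no new data. The downside is that some abnormality percentages become slightly less favourable.

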6.1 Subject Disposition

The number and percentage of subjects screened, enrolled, cohort assignment, completed treatment, completed study, and analysis populations will be summarized for each cohort, by neurodegenerative disease population, and overall. The time in study (in days) and follow-up time will also be summarized for each cohort and overall.

6.2 Protocol Deviations

The number and percentage of protocol deviations will be presented by cohort and overall.

6.3 Missing Data and Imputation

There will be no imputation of missing data.

6.4 Demographics and Baseline Characteristics

Demographic and baseline characteristics will be summarized for each cohort and overall, including age (years), sex (male, female), child-bearing potential? (Yes, No: bilateral oophorectomy, bilateral tubal ligation, hysterectomy, post-menopausal, and other), contraception (Yes, No), ethnicity (Hispanic or

Latino, Not Hispanic or Latino), Race (American Indian or Alaska Native, Asian, Black or African American, Native Hawaiian or Other Pacific Islander, White, Other), height (inches), weight (lbs), and iris color (Blue, Green, Brown, Black, Grey, Hazel, Other).

6.5 Prior and Concomitant Medications

Prior and concomitant medications will be listed by subject and coded using the World Health Organization (WHO) drug dictionary, Version September 2021, for the Safety (SAF) Population. Any medication or vaccine taken 7 days prior to study drug administration will be recorded. The number and percentage of subjects who reported taking prior and/or concomitant medications will be summarized overall. Individual subject prior and concomitant medications data will be listed.

6.6 Medical History

Medical history will be listed by subject and coded using the MedDRA, Version 25.0, using System Organ Class and Preferred Term for the Safety Population. Individual subject medical history data will be listed.

6.7 Primary (Safety) Analysis

The primary analysis for this study will assess the safety of study drug, AMDX-2011P. Adverse Events will be coded by System Organ Class and Preferred Term using MedDRA, Version 25.0. The number and percentage of subjects experiencing treatment-emergent adverse events, serious adverse events, maximum severity to study drug, and highest relationship to study drug will be summarized by cohort and listed by subject ID for both eyes. Treatment emergent adverse events and serious adverse events leading to discontinuation will also be presented by count. Treatment emergent adverse events are defined as any AEs with an onset date on or after the date of the first dose of the investigational product or is pre-existing and worsens after administration. TEAEs severity will be measured by the severity scale: mild, moderate, severe, life-threatening, and fatal. The degree of certainty of causality will be graded using the following categories: definite, probable, possible, unlikely, and not related. A line listing of all treatment emergent adverse events will be provided including as reported verbatim term, SOC, PT, onset date, end date, severity, seriousness, causality, dose level, outcome and action taken with investigational product. Subjects with 1 or more than one TEAE per system organ class and preferred term will be counted once and be reported with the highest severity. In cases where severity or relationship are missing, the most conservative approach will be taken (i.e., highest severity and assumed to be related). Laboratory evaluations, vital sign assessments, and ECG parameters will be summarized using appropriate statistics at protocol-specified time points, as well as change-from-baseline at all protocol-specified post-baseline timepoints. Non-ocular adverse events will be summarized separately and listed by subject ID for both eyes.

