8.4.4 Time Period and Frequency for Event Assessment and Follow-Up

The occurrence of an AE or SAE may come to the attention of study personnel during study visits and interviews of a study subject presenting for medical care, or upon review by a study monitor.

All AEs including local and systemic reactions not meeting the criteria for SAEs will be captured on the appropriate eCRF. Information to be collected includes event description, time of onset, clinician's assessment of severity, relationship to study product (assessed only by those with the training and authority to make a diagnosis), and time of resolution/stabilization of the event. All AEs occurring while on study must be documented appropriately regardless of relationship. All AEs will be followed to adequate resolution.

Any medical condition that is present at the time that the subject is screened will be considered as baseline and will be reported in the Medical History eCRF page, not as an AE. However, if the study subject's condition deteriorates at any time during the study, it will be recorded as an AE.

Changes in the severity of an AE will be documented to allow an assessment of the duration of the event at each level of severity to be performed. AEs characterized as intermittent require documentation of onset and duration of each episode.

The investigator will record all events with start dates occurring any time after informed consent is obtained until 7 days after the study drug administration for non-serious AEs or 30 days after the study drug administration for SAEs. At each study visit, the investigator will inquire about the occurrence of AE/SAEs since the last visit. Events will be followed for outcome information until resolution or stabilization.

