8.4.5 Adverse Event Reporting

[Table 7](#) below summarizes the different reporting periods for AEs, SAEs, and pregnancy.

Table 7 Adverse Event Reporting Periods

Type of Event	Adverse Event	Serious Adverse Event / SUSAR	Pregnancy
Reporting period	From consent until 7 days after study drug administration or until AE is resolved or no further follow-up is required. (from consent to dosing, only collect AEs related to study procedures)	From consent until: 30 days after study drug administration or until SAE is resolved or no further follow-up is required	From dosing until 30 days after study drug administration
Reporting Timelines to the Sponsor	Entered into the clinical database on an ongoing basis	Within 24 hours of the investigator's knowledge	Within 24 hours of the investigator's knowledge
Reporting Method	AE eCRF	AE eCRF and SAE form	Pregnancy Form

Abbreviation: AE, adverse event (AE); eCRF, electronic case report form; SAE, serious adverse event ; SUSAR, serious unexpected suspected adverse reaction.

Events that begin before the start of study drug but after obtaining informed consent will be recorded on the AE section of the eCRF and will be identified in the analysis as non-TEAEs.

All SAEs will be recorded and reported to the Sponsor or designee immediately and under no circumstance should this exceed 24 hours from site awareness. The investigator will submit any updated SAE data to the Sponsor or designee within 24 hours of it becoming available.

Investigators are not obligated to actively seek AEs or SAEs after conclusion of a subject's study participation. However, if the investigator learns of any SAE, including a death, at any time after a subject has completed the study, and he/she considers the event to be related to the study drug or study participation, the investigator must promptly notify the Sponsor or designee.

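### SAP 6.7 counts an adverse event that starts on Day 1 before the injection as treatment-emergent; protocol 101 section 8.4.5 does not, and SAP 1.1 does not list the difference

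*SAP*

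**What the plan says.** SAP 6.7 calls an adverse event treatment-emergent if it has "an onset date on or after the date of the first dose of the investigational product or is pre-existing and worsens after administration". The first limb is a comparison of calendar dates, and nothing in the section refers to time of day. The TEAE line listing described there has an onset date and an end date but no onset time. SAP 5.1 makes TEAEs one of the two parts of the primary endpoint; the other is SAEs.

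Protocol 101 section 8.4.5 uses a different boundary. "Events that begin before the start of study drug but after obtaining informed consent" go on the adverse event page of the eCRF and "will be identified in the analysis as non-TEAEs".

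On what is collected before dosing, Table 7 in the same section has a restriction for non-serious events: "from consent to dosing, only collect AEs related to study procedures". For SAEs it has no such restriction: "From consent until: 30 days after study drug administration or until SAE is resolved or no further follow-up is required". Section 8.4.4 is broader still: "The investigator will record all events with start dates occurring any time after informed consent is obtained".

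The only entry in SAP 1.1, where departures from the protocol are declared, is "The visit window for analysis was changed from +2 days to +6 days".

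**The concern.** An event that begins on Day 1 before the injection cannot have been caused by the drug, yet the SAP would tabulate it as treatment-emergent. The protocol says how such events are to be classed in the analysis, and the SAP's rule gives the opposite class.

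Such events are plausible. The eye examination, retinal imaging, vital signs, triplicate ECG, safety laboratory tests and first PK sample all take place before dosing on Day 1 (protocol 1.3 and 4.1). Protocol Table 2 itself names mild discomfort, tiredness and short-lived dry eye as risks of retinal imaging. These are procedure-related events of the kind that Table 7 collects before dosing.

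At stake is the TEAE count in small dose cohorts. TEAE listings also go into the interim review under SAP 7. A reader of the listing in SAP 6.7 could not spot the problem, because it shows no onset time. If severity or relationship were also missing, SAP 6.7 would report the event at the highest severity and as related. That should be uncommon, since protocol 8.4.3.2 requires a relationship assessment for every adverse event.

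**Working it through.** The check applies the two rules to each possible onset. The protocol column reads 8.4.5 literally.

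| Onset of the event | SAP 6.7 | Protocol 101, 8.4.5 |
|---|---|---|
| After consent, before Day 1, no worsening | not a TEAE | not a TEAE |
| Day 1 before injection, no worsening | **TEAE** | **not a TEAE** |
| Day 1 before injection, worse after dosing | TEAE | not a TEAE on the literal wording |
| Before Day 1, worse after dosing | TEAE | not a TEAE on the literal wording |
| After the injection starts | TEAE | TEAE |

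The second row is the conflict created by the date rule. The onset date equals the dose date, so the first limb of the SAP definition is met. The worsening limb can only add events, so it does not remove this one.

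The third and fourth rows arise from the worsening limb. That limb is a sensible extension, but 8.4.5 makes no exception for worsening, so it too goes beyond the protocol's words.

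The size for one affected subject follows from the planned cohort sizes. Inputs: 3 to 9 subjects in cohorts 1 and 2, and 12 in cohorts 3 and 4 (protocol Table 3 and SAP 3); up to 36 in all (protocol 9.1). If the subject has no other TEAE, the any-TEAE rate rises by 100 × 1/n percentage points:

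- n = 3: 100/3 = 33.3
- n = 9: 100/9 = 11.1
- n = 12: 100/12 = 8.3
- n = 36: 100/36 = 2.8

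If the subject has another TEAE, the any-TEAE rate does not move, but the line listing gains an event and a system organ class or preferred term row may gain a subject. The documents give no rate of predose events and none is assumed, so these figures illustrate scale and are not an expected bias.

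Whether the protocol's rule can be applied depends on the data. Protocol 6.4 has the study drug start time recorded in the eCRF. For adverse events, protocol 8.4.4 states: "Information to be collected includes event description, time of onset". The same section also speaks of start dates, and the eCRF was not available, so it is not certain that a clock time is captured.

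**The case against.** The strongest reply is that the practical effect is very small. Only Day 1 onsets before the injection are touched, and Table 7 limits the non-serious ones to procedure-related events. The error can only add TEAEs, so it hides no harm. SAP 6 plans no formal inference. Where causality is graded, the Definite, Probable and Possible categories in protocol 8.4.3.2 all require a plausible time sequence from administration, so a predose event should not be graded as related. All of this stands and limits the weight of the point.

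A second reply is that protocol 9.3.2 leaves further safety detail to the SAP, and a conservative date boundary is such a detail. This is weaker, because 8.4.5 already says how these events are to be classed in the analysis. A SAP may refine that, but SAP 1.1 is where the refinement should be declared.

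A third reply concerns origin. SAP 1 says that the plan serves a master protocol containing two sub-study protocols, and neither the master nor the CAA protocol was available. A reader might infer that the SAP's author silently altered the sponsor's definition. The documents do not support that: the wording may come from the master, and the mismatch would then lie between the master and protocol 101.

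A reader might also infer that the trial's primary safety result as a whole is distorted. That does not follow either. The SAE part of the SAP endpoint is unchanged, as is the protocol's own primary endpoint in section 3, which covers all adverse events. The TEAE counts differ only if a Day 1 predose event actually occurs.

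**Conclusion.** The contradiction is real and should be settled before database lock. For a Day 1 event that begins before the injection and does not worsen, SAP 6.7 and protocol 101 section 8.4.5 give opposite classes, and SAP 1.1 does not list the difference. The consequence is conditional, over-inclusive and descriptive: at most 1/n on a cohort's any-TEAE rate for each affected subject, which is noticeable only because the cohorts are small.

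The conclusion rests on a literal reading of both rules and on protocol 101 alone. It makes no claim about how often such events will occur or about how the SAP wording arose.

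**What to change.** In SAP 6.7:

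- Define a TEAE as an adverse event with onset date and time at or after the start of study drug administration, or one already present that becomes worse after it.
- Count a Day 1 event as a TEAE when its onset cannot be placed before dosing. State this as a classification default, so that it does not clash with the no-imputation rule in SAP 6.3. It matches the conservative approach already taken for missing severity and relationship, and it loses no post-dose event.
- Identify Day 1 predose events that do not worsen as non-TEAEs.
- Add onset time, or a before/after-dosing indicator, to the TEAE listing.

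In SAP 1.1, state that the worsening limb extends the literal wording of protocol 8.4.5. If the date-only rule is intended after all, keep it and declare it there as a departure from 8.4.5. Check the master and CAA protocols first, so that one definition serves both sub-studies and their pooled summaries.

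The cost is a few sentences, one listing field and slightly more programming. If the eCRF does not capture a clock time for onset, a before/after-dosing field for Day 1 events is needed, which is a database change. Without it, the default would largely reproduce the current rule.

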8.4.3 Classification of an Adverse Event

8.4.3.1 Severity of Event

AE severity will be evaluated by the investigator in accordance with the National Cancer Institute (NCI) CTCAE v5.0¹. For AEs that are not adequately addressed in the NCI CTCAE, the investigator should classify the intensity of the AE using the following guidelines:

- Grade 1: Mild: Aware of sign or symptom, but easily tolerated; no intervention needed
- Grade 2: Moderate: Discomfort enough to cause interference with usual activity, minimal non-invasive intervention indicated (e.g., short course of antibiotics)
- Grade 3: Severe: Medically significant but not immediately life-threatening; incapacitation with inability to work or do usual activity
- Grade 4: Life-threatening: Refers to an event in which the subject was at risk of death at the time of the event, as judged by the investigator; urgent/emergent intervention indicated. This category should not be used for an event that hypothetically might have caused death if it were more severe.
- Grade 5: Fatal outcome.

¹ Please refer to the CTCAE v5 at:

https://ctep.cancer.gov/protocolDevelopment/electronic_applications/docs/CTCAE_v5_Quick_Reference_5x7.pdf. Accessed March 30, 2022

It will be left to the investigator's clinical judgment to determine whether an AE is of sufficient severity to require the subject's removal from treatment or from the study. A subject may also voluntarily withdraw consent from treatment due to what she/he perceives as an intolerable AE. If either of these situations arises, the subject should be strongly encouraged to undergo an EOS assessment and be under medical supervision until symptoms cease or the condition becomes stable. An event is defined as 'serious' when it meets at least 1 of the predefined outcomes as described in the definition of an SAE, NOT when it is rated as severe.

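### SAP 6.7 would tabulate a missing adverse event severity as fatal, while SAP 6.3 says that nothing missing is imputed

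*SAP*

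**What the plan says.** SAP 6.7 (Primary (Safety) Analysis) sets the scale and the missing-data rule in one paragraph.

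- Scale: "TEAEs severity will be measured by the severity scale: mild, moderate, severe, life-threatening, and fatal". The protocol's own scale (8.4.3.1) ends in the same place: "Grade 5: Fatal outcome".
- Causality: "The degree of certainty of causality will be graded using the following categories: definite, probable, possible, unlikely, and not related".
- Counting: "Subjects with 1 or more than one TEAE per system organ class and preferred term will be counted once and be reported with the highest" (that is, at the worst grade).
- Missing items: for a blank in either field, "the most conservative approach will be taken (i.e., highest severity and assumed to be related".

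The paragraph does not exclude fatal as the imputed level and does not link the imputed level to the recorded outcome, although outcome is a separate item in the event listing. It does not say which of the five causality categories stands for related.

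SAP 6.3 (Missing Data and Imputation) is a single sentence with no exception: "There will be no imputation of missing data". Protocol 9.3.2 gives no rule for missing severity or relationship.

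**The concern.** A conservative rule for missing severity is common, but its result depends on the top of the scale. Here the top level is an outcome, death, and not a degree of intensity. Assigning it to a subject who is alive does not err on the cautious side. It records something that did not happen.

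The imputed level also dominates the table. Each subject is counted once per system organ class and preferred term at the highest severity, so an imputed fatal displaces any lower grade recorded for that subject and term. The severity table could then show a death that the outcome column contradicts.

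The incidence, nature and severity of treatment-emergent events are the primary endpoint (SAP 5.1). The study is first-in-human, with cohorts that may be as small as 3. Two sections of the SAP give opposite instructions for a primary-endpoint variable, which weakens the pre-specification that the SAP gives as its purpose.

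**Working it through.** The plan states no figure on this point, so there is none to reproduce. The check applies the 6.7 rule to the 6.7 scale and then sizes one affected record.

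**Step 1: what the rule returns.** The levels are "mild, moderate, severe, life-threatening, and fatal", so the highest is fatal. The missing-item sentence can be read in two ways:

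- *Item by item:* only the blank item is filled.
- *Joint:* a blank in either item triggers both fills.

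| Severity recorded | Relationship recorded | Item by item | Joint | If 6.3 governs |
|---|---|---|---|---|
| blank | not related | fatal, not related | fatal, related | severity stays blank |
| blank | possible | fatal, possible | fatal, related | severity stays blank |
| blank | blank | fatal, related | fatal, related | both stay blank |
| mild | blank | mild, related | fatal, related | relationship stays blank |

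A blank severity becomes fatal under both readings of 6.7. Whether the event is also related depends on the recorded relationship and on the reading. A blank relationship alone creates a fatal event only under the joint reading.

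**Step 2: size of one record.** SAP section 6 uses the number of subjects in the relevant population and cohort as the denominator. One affected subject therefore contributes 100 × 1/n percent. Cohort sizes come from SAP section 3 and totals from SAP 3.1, assuming that every subject is dosed.

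- n = 3 (smallest cohort): 100/3 = 33.3%
- n = 5 (largest planned cerebral amyloid angiopathy cohort): 100/5 = 20.0%
- n = 9 (upper size of cohorts 1–2): 100/9 = 11.1%
- n = 12 (cohorts 3–4): 100/12 = 8.3%
- n = 36 (all of AMDX-2011P-101): 100/36 = 2.8%

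These are percentages of subjects shown with a fatal event when nobody has died. They are not all related fatal events; step 1 gives the conditions for that.

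**Step 3: effect of the repair.** If fatal is used only where the recorded outcome is death, the fatal events created by imputation fall from one per subject with a blank severity to zero, and every percentage above falls to 0%.

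**The case against.** A reader might infer that any single blank field will be reported as a drug-related death. The documents do not support that, for two reasons. On the ordinary item-by-item reading, a blank severity keeps its recorded relationship and a blank relationship keeps its recorded severity. And if 6.3 governs, nothing is filled and no fatal event is created.

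The other arguments against the point are these.

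- **The specific rule may simply override the general one.** On that view, 6.3 lacks only a cross-reference. This is a fair reading, but it is also the reading under which the fatal result stands. Either way one section needs editing.
- **Highest severity may mean the highest grade already recorded.** The sentence follows the one on counting a subject at the highest severity, so a programmer could take it that way. This is less natural, and it returns no value when the blank record is the only one for that subject and term.
- **Blanks should be rare.** Severity and relationship are items to be collected for each event (Protocol 8.4.4). The data system checks for incomplete entries (10.1.8.1), missing data are queried with the sites (10.1.7), and the database is fully source verified (10.1.6). This stands, and it limits the practical risk.
- **Little depends on the table.** There is no formal inference (SAP section 6). The stopping rules in Protocol 7.1 rest on investigator and SMC judgement and not on SAP imputation. A fatal severity in a living subject would also conflict visibly with the listed outcome. This stands too: the likely harm is a conspicuous, correctable cell in a descriptive table.

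These arguments bear on how likely and how damaging the error is. They do not change what 6.7 returns when it is applied as written.

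**Conclusion.** The point holds in a limited form. If SAP 6.7 is followed, a missing severity in a living subject is tabulated as fatal. It is related as well only where the relationship is blank or already recorded as related, or under the joint reading. One record would show as 33.3% of a cohort of 3, 8.3% of a cohort of 12, or 2.8% of 36. The rule also contradicts 6.3.

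The conclusion assumes that a blank severity survives to database lock, that 6.7 takes precedence over 6.3, and that the highest severity means the top of the stated scale. The documents give no expected rate of missing severity, and the data controls suggest that it will be low. The documents do not support a prediction that a false death will be reported. They do show a stated rule that gives a wrong value for a primary-endpoint variable, next to a second rule that says the opposite. It should be corrected before database lock.

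**What to change.** In SAP 6.7:

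1. State that severity and relationship are handled separately, so that a blank in one does not alter the other.
2. Show a missing severity either in its own missing row or at a named non-fatal grade, for example severe. Both are acceptable conventions. If a missing row is used, say how a subject is counted who also has a recorded grade for the same term.
3. Use fatal only where the recorded outcome is death. A flat ban on imputing fatal would be wrong in the other direction: a real death with a blank severity would then appear at a lower grade.
4. Name the causality category used when the relationship is missing, because the highest relationship is tabulated over five categories.
5. Footnote the number of imputed values in each table, and keep the listings as reported.

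In SAP 6.3, name this rule as an exception.

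The cost is a few sentences across two SAP sections and a small change to the table programs and footnotes. No data collection or protocol change is needed.
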